6.2 Endpoint Analyses

Descriptive statistics will be computed for each treatment group. For all comparative analyses between the two treatment groups, independent samples t-test and Chi-Square test (or Fisher's exact test) will be performed for continuous variables or categorical variables, respectively. If either the normality or equal-variance assumptions underlying the traditional t-tests are violated, a non-parametric test will be used.

7. Risk Analysis

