Hyponatremia is the most common electrolyte abnormality in the hospital setting.^{1,3} Hyponatremia, based on admission values, has been associated with higher in-hospital mortality, 60-day mortality, longer length of hospital stay, and requirement for hospital readmissions.^{2,4,5} Similar findings are applicable to hospitalized HF patients as well.⁸⁻¹¹ However despite these associations, the importance of hyponatremia to influence acute treatment decisions in acute HF remains equivocal due to a lack of data. Importantly, we've recently shown that moderate to severe hyponatremia, especially <130 mEq/L, was associated with higher loop diuretic dose requirements and more frequent need for escalation of the diuretic regimen to achieve the same level of diuresis as normonatremic patients.¹⁴ Severity of hyponatremia was also associated with a greater than two-fold increase in the incidence of diuretic resistance, acute worsening renal function, sustained hypotension, increased length of stay, and in-hospital mortality. Our study results raised two important questions: 1) whether correction of hyponatremia can prevent or lower the risk of complications with conventional diuretics and 2) whether alternative treatments such as aquaretics (i.e. vasopressin receptor antagonists) represent a superior treatment modality for these patients? Data from small subgroups of hyponatremic patients in the EVEREST and ACTIV-CHF studies indicated that tolvaptan is effective at raising serum sodium and urine output in these patients.^{20,21} In addition, tolvaptan monotherapy was shown to exert a greater effect on urine volume and weight loss than a fixed dose of furosemide in stable NYHA FC II-III systolic HF patients.²³ However, these were not acutely decompensated patients, and a fixed dose of tolvaptan was being compared to fixed dose oral furosemide. Therefore, there is a **critical need to evaluate the role of aquaresis with tolvaptan as an acute treatment modality for acute HF complicated by hyponatremia**. These patients pose a particularly difficult challenge when attempting to gain effective diuresis with loop diuretics. The **purpose** of the current study is to prospectively evaluate the comparative efficacy and safety of a tolvaptan-based diuretic regimen compared to conventional diuresis with a furosemide-based regimen on short-term clinical and treatment outcomes in hyponatremic acute HF patients. Both reduced and preserved left ventricular systolic function patients will be studied.

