3.1 Trial Design

3.1.1 Design

This will be a prospective, open-label, parallel-group, randomized study comparing a tolvaptan-based aquaretic regimen to a conventional continuous infusion loop diuretic-based regimen of furosemide. The initial 24 hours of study treatment will compare tolvaptan monotherapy to furosemide monotherapy. After the initial 24 hours, treatment regimens may be altered to achieve desired clinical goals.

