3.2.2 Safety Endpoints

Primary safety endpoint:

Mean change in serum creatinine at 24 hours post randomization

Secondary safety endpoints:

GFR change at 24, 48, 96 hours, and at discharge (estimated from Scr)

Acute worsening of kidney function (increase in Scr 0.3 mg/dL or 25% above baseline)

Electrolyte abnormalities (hypokalemia, hypomagnesemia, hyper/hyponatremia)

Hypotension

Changes in plasma renin activity, copeptin, NT-proBNP, and cystatin C concentrations

In-hospital mortality

Hospital length of stay (ICU and total)

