3.3 Study Population

3.3.1 Inclusion Criteria

- Requiring hospitalization for acute HF with signs or symptoms of volume overload (i.e. elevated JVP, rales, edema)
- Serum sodium <135 mEq/L at time of or within first 48 hours of hospitalization (A maximum of 25 patients will be enrolled with serum sodium concentrations between 130 to 134 mEq/L as the inclusion).
- Randomized within 48 hours of presentation to hospital
- ≥ 18 years of age
- Informed consent

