3.4 Randomization

3.4.1 Randomization Procedure

If a patient is suitable to participate in the study and has given signed informed consent, the patient will be assigned a study number and randomized to one of the treatment arms. Randomization will occur using a computer generated randomization list prepared by the principal investigator using a 10-block scheme prior to enrollment of the first study subject. Randomization will also be stratified based on serum sodium at inclusion to 130-134 mEq/L and <130 mEq/L.

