6.1 Sample Size Calculation and Power Analysis

A total of 50 patients (25 in each group) would provide 93% power to detect a difference of 50% in urine output at 24 hours between treatments, $\alpha=0.05$. The power was calculated based on the magnitude of difference in urine output seen in the ACTIV-CHF²⁰ (24 hour mean urine output for tolvaptan was approximately $4100\pm 2100\text{mL}$ vs $2300\pm 1100\text{mL}$ compared to placebo when added to standard therapy) and in the Udelson et al²³ study (24 hour mean increase in urine output with tolvaptan monotherapy $2600\pm 1500\text{mL}$ vs $900\pm 850\text{mL}$ with furosemide). Based on our previous data demonstrating poor response to loop diuretics in the hyponatremia acute HF population, we believe a 50% difference (standard deviation of 25%) is a reasonable and conservative estimate of what the difference will likely be.

Amendment August 9, 2017:

Due to slow enrollment, we anticipate not achieving our desired sample size of 50 subjects. Our revised power calculation reveals that if we achieve a mean difference with the same magnitude standard deviation between groups (e.g. mean difference is $1000\pm 1000\text{mL}$), our power will be between 80-90% with a sample size between 34-46 subjects. Based on current rate of enrollment, it is likely that we will achieve a sample of at least 34 subjects, which should allow the results to be meaningful despite early termination of enrollment.

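### Randomization is stratified by serum sodium but the arms are compared with unstratified tests; adding the stratum is a nearly free, minor gain in power if sodium is prognostic

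*Combined protocol and SAP*

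**What the plan says.** Section 3.4.1 states: "Randomization will also be stratified based on serum sodium at inclusion to 130-134 mEq/L and <130 mEq/L". Section 3.3.1 limits the milder stratum: "A maximum of 25 patients will be enrolled with serum sodium concentrations between 130 to 134 mEq/L".

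Section 6.2, repeated in the Statistical Plan row of the synopsis, governs every between-arm comparison: "For all comparative analyses between the two treatment groups, independent samples t-test and Chi-Square test" (or Fisher's exact test) are to be used for continuous and categorical variables. The fallback is: "If either the normality or equal-variance assumptions underlying the traditional t-tests are violated, a non-parametric test will be used". That test is not named, and no stratification is mentioned for it. No section provides a stratum term, a stratified test or an adjusted model.

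The 2017 amendment in Section 6.1 takes a difference equal to one standard deviation (example 1000 ± 1000 mL) and says "our power will be between 80-90% with a sample size between 34-46 subjects". It expects to reach at least 34 subjects.

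**The concern.** The protocol treats sodium as important enough to stratify on and to cap, and then leaves it out of the analysis. Its own rationale gives a reason to expect an association. Section 2 reports that "moderate to severe hyponatremia, especially <130 mEq/L, was associated with higher loop diuretic dose requirements", and <130 mEq/L is exactly the stratification cut. Sections 1.3 and 2 also link the severity of hyponatremia to worsening renal function, which bears on the primary safety endpoint, "Mean change in serum creatinine at 24 hours post randomization".

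If sodium predicts the outcome, stratified allocation makes the true standard error of the treatment difference smaller than the one the t-test computes. The test is then conservative and gives up power. This matters most at N=34, where planned power is only just above 80%.

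**Working it through.** **Inputs from the documents.** Effect 1000 mL and SD 1000 mL (Section 6.1); N from 34 to 46; 1:1 allocation; alpha 0.05; two strata; at most 25 patients at 130-134 mEq/L.

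**Assumptions.** Two-sided test; the 10-block scheme read as permuted blocks of 10 within stratum; normal errors; 1000 mL as the total within-arm SD in both arms; stratum gaps of 0, 500 and 1000 mL, because the documents give none.

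**Step 1: reproduce the stated power.** For the two-sample t-test with n per arm, the noncentrality is (1000/1000) × √(n/2) on 2n − 2 degrees of freedom.
- n = 17: √8.5 = 2.915, df 32, power 80.7%.
- n = 23: √11.5 = 3.391, df 44, power 91.2%.

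These are the smallest arm sizes reaching 80% and 90%, so the 34-46 range follows from an unstratified t-test. The stated figure stands.

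**Step 2: what the t-test leaves in the error term.** With strata in proportions p and 1 − p and the same gap g in both arms, the stratum share of total variance is g² × p(1 − p)/SD². At a 17/17 split:
- 500 mL: 250,000 × 0.25/1,000,000 = 6.25%.
- 1000 mL: 1,000,000 × 0.25/1,000,000 = 25%.

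At 25%, the residual SD is √0.75 = 0.866 of the total. The noncentrality for a model with stratum becomes 2.915/0.866 = 3.367 on 31 df, giving power of about 90.3%. With no gap, the lost degree of freedom takes power from 80.7% to 80.6%. This approximation ignores slight imbalance from incomplete blocks, so simulation was used for the comparison.

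**Step 3: simulation, 100,000 trials per cell.** Effect 1000 mL averaged over strata. Power in %, for gaps of 0/500/1000 mL; changes were taken before rounding.

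| N (130-134 / <130) | Gap in | t-test | Treatment + stratum | Change (points) |
|---|---|---|---|---|
| 34 (17/17) | furosemide only | 80.4/81.1/81.9 | 80.2/81.2/83.6 | -0.2/+0.1/+1.7 |
| 34 (17/17) | both arms | 80.6/81.1/83.0 | 80.3/82.9/90.2 | -0.2/+1.8/+7.2 |
| 34 (25/9) | furosemide only | 80.5/80.7/81.4 | 80.4/80.8/82.6 | -0.2/+0.1/+1.2 |
| 34 (25/9) | both arms | 80.4/81.2/82.4 | 80.2/82.5/88.2 | -0.2/+1.3/+5.8 |
| 46 (25/21) | furosemide only | 91.2/91.6/92.4 | 91.2/91.7/93.3 | -0.1/+0.2/+0.9 |
| 46 (25/21) | both arms | 91.1/91.7/93.7 | 91.0/92.7/96.9 | -0.1/+1.0/+3.3 |

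Type I error at N=34 (17/17):
- Gap in both arms: t-test 5.1/4.4/2.6%, stratum model 5.1/5.0/5.0%.
- Gap in furosemide only: t-test 5.0/4.6/3.7%, stratum model 5.0/4.8/4.2%.

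The t-test is conservative whenever a gap exists and never materially above 5%.

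**Step 4: the rank fallback, N=34 (17/17).** Power in % for gaps of 0/500/1000 mL:

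| Gap in | Plain rank | Van Elteren | Aligned rank |
|---|---|---|---|
| furosemide only | 78.1/78.6/79.1 | 77.1/77.5/77.7 | 77.9/79.0/81.4 |
| both arms | 78.2/78.7/79.9 | 77.3/79.9/87.8 | 78.0/80.7/88.5 |

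Van Elteren trails the plain rank test when there is no gap and when the gap is in furosemide only. The aligned-rank form loses about 0.2 point with no gap and gains otherwise.

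**Step 5: baseline creatinine.** For the creatinine change at N=34, with no stratum gap and power near 80%, adding stratum and baseline creatinine moves power by +2.3/+0.4/-0.8 points at assumed baseline-to-24-hour correlations of 0.8/0.9/0.95.

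The t-test and stratum-model urine-output results at N=34 were confirmed by separate simulation. The rank and creatinine figures rest on one set of runs.

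**The case against.** The strongest reply is that nothing here is an error. The tests are valid, the power statement reproduces, and the benefit is negligible in the case nearest the evidence. The cited data compare hyponatremic with normonatremic patients, who are not in this trial, and describe the dose needed to reach the same diuresis, not the volume passed. They say nothing about tolvaptan response by stratum. A 1000 mL gap between two hyponatremic strata would equal the whole assumed treatment effect, and even then a furosemide-only gap yields only 1.7 points. All of this stands. It is why the point is minor and why the 7-point figure should not be read as the expected gain.

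A second reply is that the t-test may not be the test actually run. The planning data in Section 6.1 have unequal SDs (2100 vs 1100 mL; 1500 vs 850 mL). In a small simulation at the second ratio, N=34 with no gap, a Levene test rejected equal variance in about 43% of trials, which would trigger the fallback. This also stands as a reason to specify the fallback. The same simulation showed no material type I inflation for the stratum model, and the aligned-rank test shows a similar pattern: -0.2/+0.4/+2.3 points against the plain rank test for a furosemide-only gap.

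A third reply is that changing the primary test late in an open-label trial invites suspicion. That is a condition on when the change is made; it does not argue against making it while the arms are still uncompared.

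**Conclusion.** The concern holds as a minor one. The analysis does not use the strata on which patients are randomized, and using them is close to free. At N=34 the price is about 0.2 point of power if the strata do not differ. Over assumed gaps of 500 to 1000 mL at a 17/17 split, the gain is 0.1 to 1.7 points if only furosemide response differs and 1.8 to 7.2 points if both arms share the gap. Gains are smaller at N=46.

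The mismatch itself is certain. The size of the benefit is not, because it depends on a stratum difference the documents do not report, and on normal errors and equal arm SDs. The planned tests remain valid and the stated 80-90% power is unaffected.

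**What to change.** In Section 6.2 and the synopsis, prespecify for the two primary endpoints (24-hour urine output and 24-hour creatinine change) a linear model with treatment and sodium stratum as randomized, using model-based standard errors. If a rank test is kept as the fallback, name an aligned-rank (Hodges-Lehmann) test within strata. Keep the unadjusted tests as sensitivity analyses. Baseline creatinine may be added to the creatinine model, but this is optional, as are stratified secondary analyses.

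Section 3.1.1 says "This will be a prospective, open-label, parallel-group, randomized study", and the 2017 amendment anticipates stopping enrollment early. The change should therefore be dated before any comparison by arm. If outcomes by arm have already been seen, report the adjusted result as supportive.

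The cost is a wording change and one degree of freedom per primary endpoint (two for creatinine if baseline is added). No patient, visit or variable is added, since the stratum is already recorded at randomization.

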7.1 Data Safety Monitoring

The principal investigators will be responsible for monitoring adverse events which may occur during the course of the study, and determine if the benefit to risk of amending study procedures or continuing the study is appropriate in order to mitigate any unforeseen risks.

8. Drug Management

8.1 Drug Storage

All study medications will be stored by the Investigational Drug Service pharmacy.

8.2 Drug Dispensing and Tracking

The Investigational Drug Service pharmacy will maintain all records related to receipt, inventory, dispensing of the study medications.

9. Reports and Records Management

9.1 Source Documents

All source documents pertaining to the study will be maintained by the principal investigators. These include the screening log, case report forms (CRFs), informed consent forms, laboratory results, and other supporting documentation where appropriate or needed.

9.2 Data Collection

All data will be collected manually on standardized CRFs. Data from completed CRFs will be entered into a computer database.

9.3 File Management and Retention

All study documents will be retained by the principal investigators in a secured location for a minimum of 2 years after the study results have been published.

10. Ethics and Regulatory Issues

10.1 Institutional Review Board

The study will be conducted in compliance all applicable laws and regulatory requirements. The study will be submitted and approved through the Los Angeles County + University of Southern California Institutional Review Board.

10.2 Informed Consent and HIPAA

Signed written informed consent will be obtained prior to initiating any study procedure for each patient. A signed copy of the Right of Research Participants and the Informed Consent, will be provided to each study subject, one copy in the patient medical records, and one copy retained by the investigators. All study documents and procedures will be HIPAA compliant and use of protected health information will be minimized by encoding of the data.

